EMG difference scores, skin conductance responses, and US expectancy ratings from acquisition (Day 1) and generalization testing (Day 2) were subjected to separate mixed-model ANOVAs with stress, stress time point, and sex entered as categorical, between-subjects factors. Trial block (4 for acquisition; 3 for generalization) and trial type (acquisition: CS+, CS-; generalization testing: CS+, CS-, 4 generalization stimuli) were entered as within-subjects factors in these analyses.

For all statistical analyses, alpha was set at 0.05. In the case of post hoc testing, alpha was adjusted with Bonferroni corrections so that the family-wise error rate did not exceed 0.05.

A priori power analyses were performed with G*Power 3.1.9.2 (University of Kiel, Germany). The power analyses revealed that we would need approximately 565 participants to retain adequate statistical power ($1-\beta = 0.8$) to detect small-to-moderate effect sizes ($f = 0.145$) for main and interactive effects of all independent variables outlined above.

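### Post hoc family-wise error is held at 0.05 with Bonferroni; Holm's step-down procedure gives the same guarantee, is never less powerful, and would be a cheap, optional improvement.

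*Combined protocol and SAP*

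**What the plan says.** The combined protocol and SAP covers multiplicity in two sentences near the end of its Statistical analyses section. The general level is "For all statistical analyses, alpha was set at 0.05". For follow-up comparisons it adds: "In the case of post hoc testing, alpha was adjusted with Bonferroni corrections so that the family-wise error rate did not exceed 0.05".

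These comparisons follow factorial mixed-model ANOVAs, run separately for each outcome "with stress, stress time point, and sex entered as categorical, between-subjects factors". The within-subject factors for the conditioning outcomes are given as "Trial block (4 for acquisition; 3 for generalization) and trial type (acquisition: CS+, CS-; generalization testing: CS+, CS-, 4 generalization stimuli".

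The section does not say which comparisons form a family, how many there are, or what effect sizes are expected for individual contrasts. It does not use the term single-step, but that is the ordinary meaning of adjusting alpha by Bonferroni. The power statement ("we would need approximately 565 participants", for 80% power at f = 0.145) concerns the ANOVA effects, not the post hoc contrasts.

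**The concern.** The only aim stated for the post hoc adjustment is family-wise error of at most 0.05. Bonferroni tests every one of m comparisons at 0.05/m, even after some have been rejected. Holm orders the p-values and tests them in turn at 0.05/m, 0.05/(m−1), and so on up to 0.05, stopping at the first non-rejection. It meets the same aim with thresholds that are never stricter.

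This bears on the plan because a significant interaction does not show which cells or stimuli differ, so the follow-up contrasts carry much of the interpretation. The documents show no power set aside for those contrasts. If several differences in one family are real, which is plausible in a conditioning and generalization design, Bonferroni may leave some undetected that Holm would find.

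**Working it through.** **1. The plan's own figures.** With m comparisons at 0.05/m, the upper bound on family-wise error is m × 0.05/m = 0.05. Under independence it is 1 − (1 − 0.05/m)^m, which is 0.0492 for m = 3, 0.0490 for m = 6, 0.0489 for m = 15 and 0.0488 for m = 28. The plan's statement is correct.

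The sample size of 565 does not depend on the post hoc method. It can be neither confirmed nor called wrong, because numerator degrees of freedom and within-subject correlation are not given. With λ = f²N and 8 groups, 80% power needs 376 participants at 1 numerator df, 523 at 3, 573 at 4 and 690 at 7.

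**2. Why Holm has the same guarantee.** Suppose m₀ of the m null hypotheses are true. When Holm first rejects a true null, at most m − m₀ others have been rejected, so the threshold is at most 0.05/m₀. The chance that any of the m₀ true nulls has a p-value that small is at most m₀ × 0.05/m₀ = 0.05, whatever the dependence. Each Holm threshold is at least 0.05/m, so everything Bonferroni rejects is also rejected. For m = 6 the Holm thresholds are 0.0083, 0.0100, 0.0125, 0.0167, 0.0250 and 0.0500; Bonferroni uses 0.0083 throughout.

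**3. Assumptions needed for a size.** None of these is in the documents.
- Two-sided normal tests, each real difference having 80% power at an unadjusted 0.05 (mean 1.96 + 0.84 = 2.80).
- Illustrative family sizes: 3 (pairs among three blocks), 6 (pairs among four blocks), 15 (pairs among six Day 2 trial types) and 28 (pairs among the 2 × 2 × 2 = 8 between-subject cells).
- Independent tests, or a common correlation of 0.3.

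**4. Check of the simulation.** Bonferroni power per real difference is Φ(2.80 − z), with z the two-sided critical value at 0.05/m. For m = 6, z = 2.64, which gives 56.5%. The simulated values are 56.4% to 56.5% under independence.

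**5. Six comparisons: average power per real difference** (150,000 to 400,000 replicates under independence, 200,000 at correlation 0.3).

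| Real differences | Correlation | Bonferroni | Holm | Gain (points) |
|---|---|---|---|---|
| 1 of 6 | 0 | 56.5% | 56.6% | 0.1 |
| 1 of 6 | 0.3 | 56.5% | 56.6% | 0.1 |
| 3 of 6 | 0 | 56.5% | 59.7% | 3.2 |
| 3 of 6 | 0.3 | 56.3% | 59.3% | 3.0 |
| 6 of 6 | 0 | 56.4% | 68.2% | 11.8 |
| 6 of 6 | 0.3 | 56.5% | 67.4% | 10.9 |

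The chance of finding at least one real difference hardly moves, because Holm's first step is the Bonferroni threshold. Under independence it is 91.7% against 91.8% with three real, and 99.3% for both with six. At correlation 0.3 with six real it is 94.8% for both.

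**6. Other family sizes, independent tests (Bonferroni to Holm).**

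| m | One real | About half real | All real |
|---|---|---|---|
| 3 | 65.9% to 66.1% | not run | 65.9% to 75.1% |
| 15 | 44.9% to 44.9% | 44.6% to 47.3% | 44.7% to 54.2% |
| 28 | 37.4% to 37.4% | 37.4% to 39.7% | 37.4% to 44.0% |

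**7. Actual family-wise error, m = 6, independent tests.** With no real differences it is 4.9% for both methods. With one real it is 4.1% for Bonferroni and 4.6% for Holm; with three real, 2.5% and 3.7%. All are below 5%.

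**The case against.** The strongest reply is that nothing here is wrong: the plan sets a target and names a valid method that meets it. That stands.

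It is also fair that the largest gain comes from the most favourable case. Equal stress effects at every Day 2 stimulus, for example, would be a main effect of stress, which the ANOVA tests directly. Follow-up contrasts are usually run after an interaction, where effects differ between stimuli or cells. In the runs at six comparisons with one to three real differences, the gain is about 0 to 3 points.

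Bonferroni also has some advantages: one fixed threshold, simple simultaneous intervals that match the tests, and a lower actual family-wise error when some nulls are false. These are real but modest. The plan asks only for error of at most 0.05, which both methods meet, and mentions no confidence intervals for the contrasts.

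Two practical objections also stand. The families are undefined, which affects Bonferroni and Holm equally and matters more for interpretation than the choice between them. And the analysis text is in the past tense, so a later move to a more liberal rule could look data-driven.

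A reader might go further and infer that real differences are being missed for no return. The documents do not support that: with no families, contrast effect sizes or correlations between tests, no actual loss can be shown, and Bonferroni does buy the small advantages just listed.

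**Conclusion.** The point holds as an optional efficiency improvement. That Holm gives the same guarantee and never rejects less is a mathematical result and does not depend on the assumed families or effects. The size of the benefit does. With 80% unadjusted power per real contrast and six comparisons, it is about 0 points of average power with one real difference, about 3 with three, and about 11 with all six (10 to 12 across correlations of 0, 0.3 and 0.6). Across families of 3 to 28, the all-real gain under independence is about 7 to 12 points.

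The 11-point figure is the top of a range, not the expected gain for this study, and it should not be read as a flaw in the error control or the sample size.

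**What to change.** In the Statistical analyses section, replace the reference to Bonferroni corrections with: Holm step-down adjusted p-values within each post hoc family. Keep the 0.05 family-wise target. In the same edit, define a family as the set of follow-up contrasts for one significant ANOVA effect on one outcome. That definition is a proposal; the plan currently has none.

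The cost is a line or two of text and a standard software option. Simple Bonferroni simultaneous intervals would no longer match the tests exactly; they can still be shown, described as conservative. Actual family-wise error rises slightly but stays under 0.05.

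If results have already been seen, report the Holm-adjusted p-values beside the Bonferroni ones and label Holm as a change from the plan.
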